Official Title: Effect of Preoperative Dexpantenol Moisturizer on the Prevention of Angular Cheilitis After Pediatric Adenotonsillectomy: A Randomized Controlled Trial

NCT Number: NCT07002632

Document Date: July 7, 2021

MATERIALS AND METHODS

This prospective, randomized, controlled study was designed and conducted in strict adherence to the ethical principles of the Declaration of Helsinki. The study protocol was approved by the institutional ethics committee (approval date: 07.07.2021; number: 309) and written informed consent was obtained from patients' parents. This study was designed and reported in compliance with the CONSORT (Consolidated Standards of Reporting Trials) guidelines for randomized controlled trials. A CONSORT flow diagram illustrating the progress of participants through the trial phases is included (**Figure 1**). Given the limited prior literature, confined to a single pilot study by England et al. [4], a precise power analysis was not feasible. Initially, the target sample size was set at 60 patients over a 3-year period. To enhance statistical power, enrollment continued throughout the planned period, ultimately yielding a sample of 106 participants.

A total of 106 children aged 3-15 years scheduled for adenotonsillectomy between July 2021 and July 2024 at a tertiary referral ENT facility were enrolled in the study. Patients were randomized into study and control groups using computer-generated random numbers. In the study group, a water-in-oil emulsion formula containing 5% dexamethasone (Bepanthol® Derma moisturizing cream, Bayer Türk Kimya San. Ltd. Şti. İstanbul, Türkiye) was administered to both oral commissures as a moisturizer immediately before mouth gag insertion while the control group received no cream. The Brodsky Grading Scale was used to assess pre-operative tonsillar hypertrophy. Pre-operative Mallampati scores of patients were also recorded. The conventional cold steel tonsillectomy technique was preferred in all patients to ensure consistency. Under the supervision of the same senior surgeon, all surgeries were performed by the same resident. Under general anesthesia, the Boyle Davis mouth gag was inserted. The size of the tongue depressor of the Boyle Davis mouth gag was recorded. Prior to incision, the distance between the upper and lower central incisors was measured using a ruler.

Adenoideectomy was performed first using a standard curette technique under direct visualization with a mirror. Following excision of adenoid tissue, gauze packs were placed in the nasopharynx to achieve hemostasis and bipolar cautery was applied when necessary. Subsequently, tonsillectomy was performed using the cold steel dissection technique. Once the pericapsular plane was identified, the tonsils were dissected bluntly and excised. Bipolar electrocoagulation and nonabsorbable 2.0 silk ties were utilized simultaneously to manage hemorrhage in all surgeries. The inferior tonsil poles were consistently ligated with 2.0 silk ties. The surgical time was recorded. A single dose of prophylactic cefazolin sodium (25 mg/kg) was administered parenterally to all patients preoperatively, and in the postoperative period, all patients received oral paracetamol suspension (20 mg/kg) three times daily for pain control.

Postoperative evaluations were conducted by a senior surgeon who was unaware of the patients' group assignments. On the first postoperative day, patients were assessed for the presence of AC and the severity of pain. The presence of AC was assessed and recorded as either present or absent. Pain intensity was evaluated by the patients' parents by utilizing the Wong-Baker Faces Pain Rating Scale, which ranges from 0 to 10 points. All patients underwent reevaluation for the same measures on the seventh day postoperatively.

Statistical Analysis

Statistical analyses were conducted using the Statistical Package for the Social Sciences (SPSS) version 26.0 (IBM Corp., Armonk, NY, USA; RRID:SCR_002865). Categorical variables were presented as frequencies and percentages (%). Numerical variables were expressed as mean and standard deviation (SD). The comparison of categorical variables was performed using the Pearson Chi-Square test. The normality of numerical variables was assessed using the Kolmogorov-Smirnov test, and variables following a normal distribution

were compared using the Independent Samples T-Test. Binary logistic regression analysis was used to evaluate the independent effect of topical dexamethasone use on the occurrence of AC on postoperative first day and first week. Odds ratios (ORs) with 95% confidence intervals (CIs) were calculated. The model's explanatory power was assessed using Nagelkerke R². A p-value less than 0.05 was considered statistically significant.

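### Does a text dated 7 July 2021 that reports the sample reached by July 2024 put the 0.05 threshold in doubt?

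*Combined protocol and SAP*

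**What the plan says.** The header reads "Document Date: July 7, 2021". Materials and Methods gives the ethics approval as "approval date: 07.07.2021; number: 309", which is the same day.

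The text under that header looks back on the trial. It describes 106 children "scheduled for adenotonsillectomy between July 2021 and July 2024" as enrolled, and it states that "A CONSORT flow diagram illustrating the progress of participants through the trial phases is included". The Statistical Analysis section is also in the past tense: "Statistical analyses were conducted using the Statistical Package for the Social Sciences (SPSS) version 26.0".

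On sample size, Materials and Methods says that a precise power analysis was not feasible. It continues: "Initially, the target sample size was set at 60 patients over a 3-year period". The next sentence is "To enhance statistical power, enrollment continued throughout the planned period, ultimately yielding a sample of 106 participants".

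On blinding, it says: "Postoperative evaluations were conducted by a senior surgeon who was unaware of the" group assignments. The significance threshold is 0.05. No interim analysis is mentioned anywhere.

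**The concern.** A reader who trusts the header will take the chi-square test, the logistic regression and the 0.05 threshold as fixed before the first child was randomised. A text that states the final sample size cannot have been written on that date, so it is not evidence of prespecification.

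The sample size adds to the unease. The only element described as initial is the target of 60. It was passed for a statistical reason, and the text does not say when that was decided. Going past a target to gain power can be a sign of optional stopping, where the groups are compared, the result falls short, and recruitment goes on. If that had happened with an unadjusted threshold, the false-positive rate would exceed 5%. A blinded outcome assessor does not rule it out, because someone else could have held the allocation list.

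**Working it through.** **Dates.** The header and the ethics approval are both 7 July 2021. Recruitment is reported to July 2024. The text is therefore at least about three years later than its header. The match with the approval date offers an ordinary explanation: the approval date was used as the document date.

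**Sample size.** The excess over the initial target is 106 − 60 = 46 patients, and 46/60 = 77%. Neither 60 nor 106 can be re-derived, because the document gives no event rates, effect size or power.

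**Stopping rule as described.** The initial plan had two parts, 60 patients and three years. The reported recruitment window, July 2021 to July 2024, is three years. So the number was exceeded and the period was kept. A sample that ends on a calendar date set beforehand does not depend on the outcome data, and type I error is then 5%. With Pearson chi-square at 53 per arm (equal arms assumed), the size is 4.3% to 5.2% for assumed angular cheilitis rates of 10% to 50%.

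**What an undisclosed look would do.** Assume one comparison at 60 with boundary 1.96, continuing to 106 only if not significant, with boundary 1.96 again.

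- Correlation between the two test statistics: √(60/106) = 0.752.
- Overall type I error: P(|z₁| > 1.96 or |z₂| > 1.96) = 0.081 by normal theory.
- With Pearson chi-square at 30 and then 53 per arm, over the same assumed rates: 7.7% to 8.4%.

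These figures depend on an event the document does not describe.

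**Whether a stricter final threshold would help.** Two standard choices for one look at 60 are a final p of 0.030 (equal boundaries, 2.167) and a final p of 0.047 (O'Brien-Fleming type, 1.987). Each holds 5% only if its matching boundary was also used at 60: 2.167 in the first case, and 1.987/0.752 = 2.64 in the second. If 1.96 had been used at 60, that look alone would spend the full 5%:

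| Boundary at 60 | Boundary at 106 | Overall type I error |
|---|---|---|
| 1.96 | 1.96 | 8.1% |
| 1.96 | 1.987 | 7.8% |
| 1.96 | 2.167 | 6.6% |

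So if the feared look did take place, neither threshold restores 5%. If it did not, no adjustment is needed.

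**The case for a change.** The strongest reply is that the statements used to dismiss the worry, a planned period and no look described, come from the same late-written text. An account given after recruitment closed cannot certify its own history. Nor does a calendar end to recruitment show that nobody compared the groups along the way. The sponsor could settle both matters from its own records with a corrected date and a sentence or two.

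Part of this stands. The document alone does not establish prespecification, and a reader should not treat the header date as if it did. A corrected date would make the record clearer.

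The inferential part does not stand. The text is not silent on why 60 was passed: it gives power as the reason, which is a natural one when no power calculation was possible and the recruitment window was still open. It reports no look, no stop based on results and no extension of the period. Lack of proof that no look took place is not evidence that one did.

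**Conclusion.** The mismatch between date and content is real, but it is clerical, and the missing history is a gap in documentation. Read as written, recruitment ran to the end of a planned three-year period with no interim comparison. The 0.05 threshold then holds at its nominal level, and no analysis, result or conclusion would change.

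The figure of about 8.1% applies only under an assumed unadjusted look at 60, with continuation on a non-significant result. Nothing in the document points to that. Even then, a final threshold of 0.030 or 0.047 would leave the error at 6.6% or 7.8%, so an altered threshold offers no gain.

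This conclusion rests on taking the document's account of recruitment at face value. The fair caution for a reader is to take 7 July 2021 as the approval date and not to cite this text as proof of what was fixed in advance. No change to the plan is called for.

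### Was the surgeon who read angular cheilitis unaware of group, given that one senior surgeon supervised every operation?

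*Combined protocol and SAP*

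**What the plan says.** All the relevant statements are in Materials and Methods.

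- **Surgery:** "Under the supervision of the same senior surgeon, all surgeries were performed by the same resident".
- **Intervention:** the cream was "administered to both oral commissures as a moisturizer immediately before mouth gag insertion while the control group received no cream". There was no placebo cream.
- **Outcome assessor:** "Postoperative evaluations were conducted by a senior surgeon who was unaware of the" group to which each patient belonged.
- **AC outcome:** "The presence of AC was assessed and recorded as either present or absent", on the first and seventh postoperative days.
- **Pain:** "Pain intensity was evaluated by the patients' parents by utilizing the Wong-Baker Faces Pain Rating Scale".
- **Allocation:** "Patients were randomized into study and control groups using computer-generated random numbers".

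The document does not name the assessor's role beyond senior surgeon. It does not say who applied the cream, who was present at that moment, how the assessor was kept unaware, or whether parents knew the group. Under Statistical Analysis, AC on day 1 and at one week is the outcome of the logistic regressions, and the significance rule is "A p-value less than 0.05 was considered statistically significant".

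**The concern.** Two roles carry the same title. One senior surgeon oversaw every operation, and the cream was given or withheld at the operating table with nothing to mask the difference. A senior surgeon also read the outcome. A reader who takes these to be one person will conclude that the assessor could have seen each child's allocation and that the claim of unawareness fails.

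The stakes would be real. AC is the outcome in the trial's title, it is a yes/no visual judgement, and no diagnostic criteria are given. Assessor unawareness is the only stated safeguard against detection bias in the AC reading. Randomization, a single operator and a uniform technique guard against other things. Neither the chi-square test nor the logistic regression can undo a difference between arms in how AC was called. Parents' pain scores raise a similar question, since their knowledge of allocation is not described.

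**Working it through.** **Step 1. Do the passages contradict each other?**

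- In the surgical description, *the same senior surgeon* stands beside *the same resident*. Both phrases say that personnel did not vary from one operation to the next. Neither looks forward to the outcome assessment.
- The assessor is introduced with an indefinite article, as *a* senior surgeon. That fits a second person at least as well as it fits the supervisor.
- If there were two surgeons, every statement is compatible with every other.
- If there was one, unawareness would be hard to sustain, though not strictly impossible, because the document does not say who was present when the cream was applied.

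The text does not decide between the two cases. A contradiction needs an assumption that the document does not make.

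**Step 2. What would biased readings do?**

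The document gives a total of 106 children but no arm sizes, AC rates or misclassification rates, so there is no figure in the plan to reproduce. Everything below except the total and the 0.05 level is assumed.

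- Arm size: n = 106 / 2 = 53, assuming equal arms.
- AC rate p = 0.30 or 0.20, with no true effect.
- Differential calling: recorded rates of p + d/2 (control) and p − d/2 (cream), so that d is the gap between arms.
- Test: uncorrected Pearson chi-square at 0.05, enumerated exactly over all pairs of binomial counts.

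| Gap d | False-positive rate, p = 0.30 | False-positive rate, p = 0.20 |
|---|---|---|
| 0 | 5.2% | 5.1% |
| 5 points | 9.0% | 10.0% |
| 10 points | 20.7% | 25.4% |
| 15 points | 40.1% | 49.9% |

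In children, a 10-point gap moves each arm by 0.05 × 53 = 2.65, which is a net difference of 0.10 × 53 = 5.3 between arms.

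As a reference point, take 16/53 with AC in the control arm. With 8/53 in the cream arm, chi-square = 3.45 and p = 0.063. With 7/53, the pooled rate is 23/106 = 0.217, the difference is 9/53 = 0.170, and chi-square = 0.170² / (0.217 × 0.783 × 2/53) = 4.50, so p = 0.034.

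**Step 3. What do the figures establish?**

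They show that a test on 106 children is sensitive to a modest difference in how AC is called. The gap d is an input, chosen by whoever runs the calculation. Nothing in the document indicates that d differs from zero, and the statement that the assessor was unaware says that it should not.

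**The case for a change.** The strongest case for acting is that silence is not reassurance. The document claims compliance with CONSORT, so a reader may fairly expect to learn who was blinded and how. Two roles share one title, there is no placebo, AC is a judgement without stated criteria, and it is the central outcome. One sentence would settle the matter. If one person did both jobs and saw the allocation, the word unaware should not stand and AC should be described as an unblinded assessment.

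Most of that stands as a point about reporting. A report of the trial should say whether the assessor was a different surgeon who was absent when the cream was given or withheld, and whether parents knew the group. It does not show a fault in the plan. The plan calls for an unaware assessor, which is what a reviewer would ask for. Re-rostering surgeons would add nothing to that requirement, and it would come too late: the document describes enrolment, in the past tense, as running from July 2021 to July 2024. The missing AC criteria and the parents' knowledge of group are separate gaps in description and say nothing about who the assessor was.

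**Conclusion.** The concern does not hold as a conflict. The passages agree if the supervising and assessing surgeons were different people, and the document nowhere says they were the same. As written, AC is read by an assessor unaware of group, which is the right design for a comparison without placebo. What remains is a gap in detail that the authors can fill from their own knowledge of who did what. No change to the design or the analysis follows.

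The illustrative false-positive rates (up to 20.7% at 30% AC, or 25.4% at 20% AC, for a 10-point gap) rest wholly on assumed equal arms, assumed AC rates and an assumed gap. They show why the detail is worth reporting; they do not measure any bias in this trial. The conclusion would change only if it emerged that the supervising surgeon made the AC readings after seeing allocation.

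### Does the pain score need a named fallback test and a planned confidence interval at day 1 and day 7?

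*Combined protocol and SAP*

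**What the plan says.** Pain is rated by parents, "utilizing the Wong-Baker Faces Pain Rating Scale, which ranges from 0 to 10 points", on the first postoperative day. The day-7 visit repeats it: "All patients underwent reevaluation for the same measures on the seventh day postoperatively".

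The Statistical Analysis section treats numerical variables in four steps:

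- Description: "Numerical variables were expressed as mean and standard deviation (SD". This carries no condition on normality.
- Check and test: "The normality of numerical variables was assessed using the Kolmogorov-Smirnov test, and variables following a normal distribution" and, after a line break in the extracted text, "were compared using the Independent Samples T-Test". The two pieces form one sentence, so no fallback was lost at the break.
- Threshold: "A p-value less than 0.05 was considered statistically significant".
- Intervals: "Odds ratios (ORs) with 95% confidence intervals (CIs) were calculated". This follows the logistic regression sentence, whose only outcome is angular cheilitis.

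Chi-square is assigned to categorical variables, so on the natural reading it does not cover the pain score.

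**The concern.** Two things look missing for pain, the only postoperative outcome besides angular cheilitis.

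First, the t-test is reserved for variables that pass the normality check, and the plan stops there. A coarse 0-10 score can easily fail such a check, most of all at day 7 if many children score near zero. If the test were picked after seeing the results, the false-positive rate could rise.

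Second, no between-arm difference or interval is named. The Materials and Methods section gives no power calculation, so no planned detectable difference helps a reader interpret a non-significant pain result. If only a p-value were printed, the reader could not tell a result that rules out a difference of about a point from one that is merely imprecise.

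**Working it through.** The plan states no figure for pain, so there is none to reproduce. The check is whether either gap could change a result or hide one.

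**Inputs.** From the document: "ultimately yielding a sample of 106 participants"; the 0-10 scale; the 0.05 threshold; mean and SD for numerical variables. Assumed, because the readable text does not give them: arm sizes of 53/53 or 46/60, and the score distributions and SDs.

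**1. Can the interval be recovered?** The 95% interval for a difference in means is

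d ± t × s × √(1/n₁ + 1/n₂),

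where d is the difference of the two reported means, s the pooled SD from the two reported SDs, and t the 97.5% point on n₁ + n₂ − 2 degrees of freedom.

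- 53/53: √(2/53) = 0.194; t on 104 df = 1.983; half-width = 1.983 × 0.194 × s = 0.385 × s.
- 46/60: √(1/46 + 1/60) = 0.196; half-width = 1.983 × 0.196 × s = 0.389 × s.

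| SD | half-width at 53/53 (points) |
|---|---|
| 1 | 0.39 |
| 1.5 | 0.58 |
| 2 | 0.77 |
| 2.5 | 0.96 |
| 3 | 1.16 |

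Everything except the arm sizes is already a planned output. The Materials and Methods section says a CONSORT flow diagram is included as Figure 1. That figure is not visible in the text available here, but such a diagram normally carries the arm sizes. All patients are said to have been re-evaluated at day 7, so the same sizes serve both visits.

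**2. Is the ordinary interval valid for a non-normal score?** It was checked by simulating 10,000 trials per setting at both splits. Seven score distributions were used: normal scores (mean 4.5, SD 2.3; mean 5, SD 3; mean 1, SD 1.5), each rounded to steps of 1 or 2 and clipped to 0-10, plus one zero-heavy distribution in steps of 2. Coverage of the t interval was 0.946-0.962, so it stands whichever test supplies the p-value.

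**3. Will a fallback be needed?** Quite possibly. With no true difference, the Lilliefors-corrected check fails in at least one arm in 73-100% of trials; the uncorrected check does so in 2-100%. The document does not say which version was used.

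**4. Does the missing fallback matter?** Type I error in the same simulations (Monte Carlo standard error about 0.002):

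| Rule | Type I error |
|---|---|
| t-test always | 0.046-0.053 |
| Mann-Whitney always | 0.045-0.053 |
| Mann-Whitney if the check fails, otherwise t-test | 0.045-0.053 |
| Better of the two p-values | 0.051-0.068 |

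For assumed differences of 0.58-1.35 points, power under the switching rule lay between 1.3 percentage points below and 4.1 above the t-test. The two tests gave different verdicts in 1.0-3.4% of trials with no difference and in 3.2-11.6% with one.

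**The case for a change.** The strongest case for acting is the interval. Among simulated non-significant trials with no true difference, the interval still reached beyond 1 point (an illustrative mark, not a clinical one) in 73-99.8% when the SD was 2.2-2.8, but in only 0.2-2.5% when it was 1.2-1.3. So the same p-value above 0.05 can mean very different things.

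That is true of a bare p-value, but the plan does not leave a bare p-value. It gives the means and SDs, and it is the SD that separates those two situations. The percentages describe the precision of 106 children at a given SD, and printing the interval would not change them. Where the t-test applies, the contrast is already implied: that test compares two means.

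On the test, it is fair to say that the wording leaves room for choice, that the two tests can disagree on a borderline result, and that nothing shows when the choice was made. However, the rise above 0.05 needs someone to report the more favourable of two tests, and the document gives no sign of that. The sentence can also be read as saying that every numerical variable passed, although it does not state this. Enrolment is already reported as complete, so no sentence added now could fix the choice in advance.

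What stands is modest: a report that names the pain test and prints the difference with its interval is easier to read. There is no similar case for the other numerical variables, such as surgical time, which are not named as outcomes.

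**Conclusion.** The concern describes the text correctly but calls for no change. The omitted fallback is one that analysts fill routinely, with Mann-Whitney. Doing so holds type I error at 0.045-0.053 and costs at most 1.3 percentage points of power against the t-test. The omitted interval follows from planned summaries plus arm sizes, at about 0.385 × SD for 53 per arm, and is valid even for coarse or skewed scores. Following the plan as written would not produce a wrong pain conclusion. Pain is not labelled primary, and the angular cheilitis odds ratios and their intervals are untouched.

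This rests on assumed arm sizes (53/53 and 46/60) and assumed score distributions, since the readable text gives neither. It also assumes that the arm sizes appear in the report and that one test, not the better of two, was used for pain. Naming that test and printing the interval at each visit is an optional reporting note.

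### No test is named for pain, and the only method offered for a numerical variable leaves out age, which could give some precision at almost no cost

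*Combined protocol and SAP*

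**What the plan says.** The Materials and Methods section describes the population as follows: "A total of 106 children aged 3-15 years scheduled for adenotonsillectomy". On allocation it says only: "Patients were randomized into study and control groups using computer-generated random numbers". It gives no allocation ratio, arm sizes, stratification or balancing by age.

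Pain is measured in this way: "Pain intensity was evaluated by the patients' parents by utilizing the Wong-Baker Faces Pain Rating Scale, which ranges from 0 to 10 points". It is recorded on the first postoperative day and again a week later: "All patients underwent reevaluation for the same measures on the seventh day postoperatively".

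The Statistical Analysis section does not mention pain by name. Its rule for numerical variables is one sentence in two parts. The first part is the condition: "The normality of numerical variables was assessed using the Kolmogorov-Smirnov test, and variables following a normal distribution". The second is the test for variables that meet it: they "were compared using the Independent Samples T-Test". Nothing is said about variables that fail the check. The only model is a binary logistic regression for AC on the first day and at the first week. The significance rule is: "A p-value less than 0.05 was considered statistically significant". No primary outcome is named, and no SD of pain, target difference or age-pain correlation is given.

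**The concern.** Ages run over twelve years, and parents rate pain across that whole range, so part of the spread in scores between children may follow age. Age is fixed before randomisation and available for every child. A comparison that includes it estimates the same arm effect and can have a smaller standard error. The plan uses a regression for AC but describes nothing similar for pain.

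At stake is the width of the confidence interval for pain on days 1 and 7. The Materials and Methods section says that no precise power analysis was feasible and that enrolment went past the target of 60, to 106, to gain power. Age adjustment serves the same aim without any more children.

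**Working it through.** The plan gives no power figure for pain, so there is nothing to reproduce. The check has two parts.

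**1. Which analysis would pain receive?** If pain passes the Kolmogorov-Smirnov check, the rule leads to an unadjusted t-test. If it fails, no test is given. Neither route includes age.

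The second route is a real possibility. Normal scores (assumed mean 5, SD 1.5 to 2.5) were simulated and rounded to 0, 2, ..., 10; the six steps are also an assumption. They failed the check in 100% of simulated samples of 106. In samples of 53 they failed in 54% to 100%, depending on the SD and on whether the Lilliefors correction was used.

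**2. What could age adjustment gain?**

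Inputs:
- Total N = 106 (Materials and Methods).
- Significance level 0.05 (Statistical Analysis); two-sided is assumed.
- 53 per arm: assumed, since no ratio is given.
- True difference 1.0 point and SD 2.0: assumed.
- R², the share of within-arm pain variance explained by age: assumed, 0 to 15%.
- No dropout: assumed.

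Formulas:
- Unadjusted SE = 2.0 × √(2/53) = 0.389.
- Adjusted SE = 0.389 × √(1 − R²).
- Power from the noncentral t distribution with noncentrality 1.0/SE, on 104 df unadjusted and 103 df adjusted.
- Equivalent extra children = 106/(1 − R²) − 106.

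| R² | Correlation | SE | Power | Equivalent extra children |
|---|---|---|---|---|
| 0 | 0 | 0.389 | 72.2% | 0 |
| 1% | 0.10 | 0.387 | 72.7% | 1.1 |
| 5% | 0.22 | 0.379 | 74.4% | 5.6 |
| 10% | 0.32 | 0.369 | 76.7% | 11.8 |
| 15% | 0.39 | 0.358 | 79.0% | 18.7 |

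The cost when age is not prognostic is small. At R² = 0, moving from 104 to 103 df leaves power at 72.2%. Estimating the age coefficient also inflates the variance by a factor of about 1 + 1/102 = 1.0098, or roughly 1%, which the table leaves out. Including it at R² = 1% gives 0.99 × 1.0098 = 0.9997, so that case about breaks even.

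**The case against.** The strongest objection is that this is a preference for efficiency and not an error. Under randomisation the unadjusted comparison is valid. The documents give no age-pain correlation, so the gain may be nil. Pain is not the outcome in the title, which is AC. All of that stands, and it limits the point to an optional improvement.

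A reader might infer three stronger things that the documents do not support.

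- **That pain will be t-tested.** The test applies only to variables that pass the normality check, and a coarse faces score may well fail it.
- **That precision is certainly being lost.** This depends on the unknown R². At 0 nothing is lost, and at 1% the gain is at most about half a point of power.
- **That a chance age difference between arms is a further harm.** If ages were spread evenly over 3 to 15 (assumed; SD 12/√12 = 3.46 years), the SE of the difference in mean age would be 3.46 × √(2/53) = 0.67 years, and a gap above one year would have a probability of about 14%. But the unadjusted standard error already allows for such chance differences. Counting them again would double the same loss.

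Timing is also a fair objection. The text reports enrolment as finished and the analyses in the past tense. An adjusted estimate introduced after the results were known, and put in place of the unadjusted one, would be a post hoc change of the headline analysis. That is a reason to report both and label the adjusted one, not a reason to leave age out.

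**Conclusion.** The point holds as a minor, nearly free improvement. The plan names no pain analysis. The one method it offers for a numerical variable is unadjusted and conditional on a normality check, and no analysis of pain uses age. The consequence is a possible loss of precision, with no bias.

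Under the assumed inputs, adjustment is worth between nothing and about 7 points of power (72% to 79%) as R² goes from 0 to 15%. Confidence in any particular gain is low, because the R², the SD, the difference and the arm sizes are all assumptions. The recommendation does not depend on one value: the loss if age is unrelated to pain is about 1% in variance.

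**What to change.** Name the pain analysis in the Statistical Analysis section. For pain at day 1 and at day 7, fit a linear model with arm and age (continuous), with robust standard errors, whether or not the score passes the Kolmogorov-Smirnov check. Report the adjusted arm difference with its 95% CI beside the unadjusted difference. This also fills the gap for a score that fails the check.

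If outcome data have already been seen, label the adjusted analysis as not pre-specified.

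The cost is a short addition to the plan, one model per visit and one degree of freedom. No further children or data are needed, since age is already known for every child.

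### The first-week model is described as testing occurrence of AC, but on the direct reading its outcome is AC present on day 7, so its odds ratio mixes prevention with healing

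*Combined protocol and SAP*

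**What the plan says.** The title gives the aim as prevention: "Effect of Preoperative Dexpantenol Moisturizer on the Prevention of Angular Cheilitis After Pediatric Adenotonsillectomy". The cream "was administered to both oral commissures as a moisturizer immediately before mouth gag insertion while the control group received no cream", so it is applied once, before the injury.

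The account of the postoperative evaluations in Materials and Methods describes two examinations. For day 1: "On the first postoperative day, patients were assessed for the presence of AC and the severity of pain". On coding: "The presence of AC was assessed and recorded as either present or absent". For day 7: "All patients underwent reevaluation for the same measures on the seventh day postoperatively".

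The Statistical Analysis then describes the model: "Binary logistic regression analysis was used to evaluate the independent effect of topical dexamethasone use on the occurrence of AC on postoperative first day and" the first week. It thus names the outcome of the logistic regression as "occurrence of AC on postoperative first day and first week".

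No other AC variable is described. There is no onset or healing date, no outcome combining the two visits, no outcome for AC that is new since day 1, and no rule for a child whose day-1 AC has gone by day 7. Neither visit is named as primary.

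**The concern.** Occurrence means that the child developed AC. Presence on day 7 is a different quantity: day-1 AC that has not yet healed, plus AC that has appeared since. A child who had AC on day 1 and recovered did develop it, yet enters the first-week model on the same footing as a child who never had it.

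The design makes the distinction matter. The cream is given once, just before the gag goes in, so a preventive effect should act at the start. Day-7 status also reflects the following six days of healing.

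Read as a result about prevention, the first-week odds ratio can therefore err either way. A cream that prevents AC may look ineffective at one week because the control children have recovered. A cream that prevents nothing but speeds recovery may look preventive.

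**Working it through.** The mismatch follows from the text and needs no assumed rate. The plan has no calculated power or AC rate to reproduce, so the arithmetic below only illustrates what the mismatch could do.

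**From the documents.** Total sample 106; significance at p < 0.05; Pearson chi-square for categorical comparisons.

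**Assumed.** 53 children per arm (106/2; arm sizes are not given), a two-sided test, and all AC, healing and new-onset rates. Power is for the unadjusted chi-square test, by exact enumeration of the two binomial counts.

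**Formulas.** With p = day-1 AC rate, h = share of day-1 AC healed by day 7, and w = rate of new AC by day 7 among children free of it on day 1:
- AC present on day 7 = p(1 − h) + (1 − p)w
- AC at either visit = p + (1 − p)w

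The healing term h enters the first expression and not the second.

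**Case 1: real prevention, equal healing.** p = 0.40 control v 0.20 cream, h = 0.70 in both arms, w = 0.05.
- Day 7, control: 0.40 × 0.30 + 0.60 × 0.05 = 0.15
- Day 7, cream: 0.20 × 0.30 + 0.80 × 0.05 = 0.10
- Either visit, control: 0.40 + 0.60 × 0.05 = 0.43
- Either visit, cream: 0.20 + 0.80 × 0.05 = 0.24

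| Outcome | Control | Cream | Odds ratio | Power |
|---|---|---|---|---|
| AC on day 1 | 40% | 20% | 0.375 | about 63% |
| AC at either visit | 43% | 24% | 0.42 | about 56% |
| AC present on day 7 | 15% | 10% | 0.63 | about 12% |

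As healing goes from 30% to 90% in both arms, the day-7 odds ratio moves from 0.49 to 0.85 and its power falls from about 35% to 5%. The day-1 and either-visit rows do not change.

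**Case 2: real prevention, unequal healing.** p = 0.40 v 0.20, w = 0, h = 0.70 control v 0.40 cream. Day-7 AC is 0.40 × 0.30 = 0.12 v 0.20 × 0.60 = 0.12, odds ratio 1.00. The preventive effect has disappeared from the day-7 result.

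**Case 3: no prevention, faster healing with cream.** p = 0.40 in both arms, w = 0, h = 0.40 control v 0.80 cream. Day-7 AC is 0.40 × 0.60 = 0.24 v 0.40 × 0.20 = 0.08, odds ratio 0.28. The day-7 test is significant in about 63% of trials, although the same share of children in each arm developed AC.

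**The case against.** **The day-1 model already tests prevention.** This stands. If the effect falls at the start, day 1 is where it shows. In Case 1 the day-1 analysis has the highest power of the three, and in Case 3 it would correctly tend to show no difference. A reader might infer that the trial has no sound test of prevention; the documents do not support that. What remains is that one sentence gives both odds ratios the same meaning, and no primary visit is named that would rank the first-week result below day 1.

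**Day-7 presence is a legitimate outcome.** This also stands. Whether a child has AC a week after surgery matters to patients, and comparing the arms on it is protected by randomisation. It would be wrong to infer that the comparison is biased or should be dropped. The fault lies in the label and in what is concluded from it.

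**The coding is inferred.** The first-week variable is not written out, and the phrase could be meant as cumulative. Nothing says so, and repeating the same present-or-absent measure on day 7 points the other way. Either way, the variable needs a definition.

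**The power contrast flatters the either-visit outcome.** It does if only 56% v 12% is shown. Against the planned day-1 model the change is from 63% to 56%, a small loss, because new onset at the same rate in both arms dilutes the difference. With no new onset the two outcomes are identical.

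**Some mechanisms are speculative.** One might argue that lip care given after AC is found on day 1 narrows the day-7 gap further. The documents describe no such care, and the point does not rely on it. Likewise, nothing in the documents shows that one preoperative application changes healing; Cases 2 and 3 show only what would follow if healing differed.

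**Conclusion.** The point holds for the first-week model only. On the direct reading of the plan, that model tests AC present on day 7, and its odds ratio cannot by itself support a statement about prevention. The day-1 model is largely untouched, and the day-7 comparison is valid for prevalence.

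The real size is unknown, because the documents give no AC, healing or new-onset rates. Under the assumptions shown, equal healing leaves the day-7 test with about 5% to 35% power for a preventive effect that the day-1 test detects about 63% of the time. A pure difference in healing of 40% v 80% yields a significant day-7 result in about 63% of trials. This merits a change of definition and wording; it does not undermine the trial.

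**What to change.** In the Statistical Analysis:

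1. Define *AC at day 1 or day 7* and use it, beside the day-1 model, for any prevention conclusion over the first week.
2. Keep the day-7 comparison, label it *AC present on day 7 (persistent or new)*, and draw no prevention conclusion from it alone.
3. Show day-1 by day-7 status in a cross-table by arm, so that new, persistent and healed AC are visible. Healing among children with day-1 AC should be descriptive only, because that subgroup forms after randomisation.

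The cost is one derived variable, one table and a change of wording, all from data already collected, with no extra visit or patient. The downside is that the either-visit outcome overlaps heavily with day 1: it is not independent confirmation and need not have more power. What it adds is that it counts AC first seen on day 7 and does not credit healing as prevention. It still misses AC that appears and clears between the two visits.
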